4) Total platelet count: There was high significant difference between the three groups regarding total platelet count ($p < 0.001$). Applying Conover test reveal; significant difference between SPE/HELLP and control, between TTP/HUS and control and between SPE/HELLP and TTP/HUS (**Table 16**), (**Figure 19**).

5) Immature platelet count A-IPC : There was significant difference between the three groups regarding immature platelet count ($p < 0.05$). Applying Conover test reveal; significant difference between SPE/HELLP and control, between TTP/HUS and control (**Table 16**), (**Figure 20**).

6) Immature platelet fraction IPF-%: There was high significant difference between the three groups regarding immature platelet fraction ($p < 0.001$). Applying Conover test reveal; significant difference between SPE/HELLP and control, between TTP/HUS and control and between SPE/HELLP and TTP/HUS (**Table 16**), (**Figure 21**).

Table (16): Total platelet count, immature platelet count, and immature platelet fraction in patients with SPE/HELLP or TTP/HUS and normal controls

Assessment of Immature Platelet Fraction in Pregnancy-Associated Thrombotic Microangiopathy: (Results)

Variable	SPE/HELLP (n=24)	TTP/HUS (n=13)	Control (n=20)	χ^2	DF	P-value
Total platelet count (*1,000/mm³)	121 (73 – 188.5) [†]	53.0 (37.0 – 81.0) ^{†‡}	269.5 (235.0 – 337.0)	35.333	2	<0.0001
Absolute Immature platelet count (*1,000/mm³) (A-IPC)	14.875 (11.781 – 22.151) [†]	11.64 (6.410 – 21.238) [†]	21.992 (16.945 – 25.431)	10.362	2	0.006
Immature platelet fraction (%) (IPF-%)	13.0 (9.6 – 22.9) [†]	19.5 (15.1 – 27.7) ^{†‡}	7.2 (6.2 – 11.1)	18.897	2	<0.0001

Data are median (interquartile range).

[†]P-value <0.05 versus Control group (Conover test).

[‡]P-value <0.05 versus SPE/HELLP group (Conover test).

[figure not shown]

Figure (19): Box plot showing the total platelet count in patients with SPE/HELLP or TTP/HUS and normal controls.

Assessment of Immature Platelet Fraction in Pregnancy-Associated Thrombotic Microangiopathy: (Results)

[figure not shown]

Figure (20): Box plot showing the immature platelet count (IPC) in patients with SPE/HELLP or TTP/HUS and normal controls.

[figure not shown]

Figure (21): Box plot showing the immature platelet fraction (IPF) in patients with SPE/HELLP or TTP/HUS and normal controls.

Assessment of Immature Platelet Fraction in Pregnancy-Associated Thrombotic Microangiopathy: (Results)

- **Prevalence of a low platelet count (A-IPC):** There was high significant difference between the three groups regarding prevalence of a low platelet count ($P < 0.001$) (Table 17), (Figure 22).
- **Prevalence of high IPF-%:** There was significant difference between the three groups regarding prevalence of high IPF ($P < 0.05$) (Table 17), (Figure 22).
- **Prevalence of high schistocyte count:** There was high significant difference between the three groups regarding prevalence of high schistocyte count ($P < 0.001$) (Table 17), (Figure 22).

Table (17): Prevalence of a low platelet count, high IPF, or high schistocyte count among patients with SPE/HELLP or TTP/HUS and normal controls

Variable	SPE/HELLP (n=24)	TTP/HUS (n=13)	Control (n=20)	P-value¶
Low total platelet count ($< 100,000/\text{mm}^3$)	9 (37.5%)	11 (84.6%)	0 (0.0%)	< 0.001
High IPF-% ($> 11.2\%$) (Machin, 2010)	14 (58.3%)	10 (76.9%)	5 (25.0%)	0.008
High schistocyte count ($> 1\%$) (Gina et al., 2011)	14 (58.3%)	11 (84.6%)	0.01 (0.0%)	< 0.001

Data are number (%).

¶Fisher's exact test.

Assessment of Immature Platelet Fraction in Pregnancy-Associated Thrombotic Microangiopathy: (Results)

[figure not shown]

Figure (22): Prevalence of a low platelet count, high IPF, or high schistocyte count among the studied groups.

✚ Receiver-operating characteristic (ROC) curve analysis

Table (18): Receiver-operating characteristic (ROC) curve analysis for discrimination between patients with TTP/HUS or SPE/HELLP using the IPF or schistocytes count

Index	Marker
-------	--------

Assessment of Immature Platelet Fraction in Pregnancy-Associated Thrombotic Microangiopathy: (Results)

	IPF	Schistocyte count
Positive group (TTP/HUS)	13 (35.1%)	13 (35.1%)
Negative group (SPE/HELLP)	24 (64.9%)	24 (64.9%)
Area under the ROC curve (AUC)	0.692 (0.519 to 0.833)	0.771 (0.603 to 0.893)
z statistic	2.028	3.022
P-value	0.043¶	0.003¶
Associated cut-off criterion	>15.9 %	>4.6 %
Sensitivity (%)	76.92 (46.2 - 95.0)	61.54 (31.6 - 86.1)
Specificity (%)	66.67 (44.7 - 84.4)	91.67 (73.0 - 99.0)
Positive predictive value (PPV, %)	55.6 (30.8 - 78.5)	80.0 (44.4 - 97.5)
Negative predictive value (NPV, %)	84.2 (60.4 - 96.6)	81.5 (61.9 - 93.7)

Diagnostic indices are presented as value (95% CI).

¶DeLong method.

- **(ROC) curve analysis for discrimination between patients with TTP/HUS or SPE/HELLP using the IPF-%:** The optimal cutoff values for IPF-% for discrimination between patients with TTP/HUS or SPE/HELLP was >15.9 %. The sensitivity and specificity were 76.92% and 66.7%, respectively. The positive predictive value (PPV) and negative predictive value (NPV) were 55.6 % and 84.2%, respectively (AUC=0.692) (**Table 18**) (**Figure 23**).

Assessment of Immature Platelet Fraction in Pregnancy-Associated Thrombotic Microangiopathy: (Results)

[figure not shown]

Figure (23): Receiver-operating characteristic (ROC) curve analysis for discrimination between patients with TTP/HUS or SPE/HELLP using the IPF.

Assessment of Immature Platelet Fraction in Pregnancy-Associated Thrombotic Microangiopathy: (Results)

- **(ROC) curve analysis for discrimination between patients with TTP/HUS or SPE/HELLP using the schistocyte count:** The optimal cutoff values for schistocyte count for discrimination between patients with TTP/HUS or SPE/HELLP was $>4.6\%$. The sensitivity and specificity were 61.54% and 91.67% , respectively. The positive predictive value (PPV) and negative predictive value (NPV) were 80% and 81.5% , respectively (AUC=0.771) (Table 19), (Figure 24).

[figure not shown]

Figure (24): Receiver-operating characteristic (ROC) curve analysis for discrimination between patients with TTP/HUS or SPE/HELLP using the schistocyte count.

Comparison of the receiver-operating characteristic (ROC) curves:

Comparison of the receiver-operating characteristic (ROC) curves between IPF-% or schistocyte count revealed no significant difference between IPF-% and schistocyte count regarding discrimination between patients with TTP/HUS or SPE/HELLP (P-value >0.05) (Table 19), (Figure 25).

Assessment of Immature Platelet Fraction in Pregnancy-Associated Thrombotic Microangiopathy: (Results)

Table (19): Comparison of ROC curves for discrimination between patients with TTP/HUS or SPE/HELLP using the IPF or schistocyte count

Index	IPF	Schistocyte count	Difference	z	P-value¶
Area under ROC (AUC)	0.692 (0.519 to 0.833)	0.771 (0.603 to 0.893)	0.079 (-0.171 to 0.328)	0.617	0.537

Diagnostic indices are presented as value (95% CI).

¶DeLong method.

Assessment of Immature Platelet Fraction in Pregnancy-Associated Thrombotic Microangiopathy: (Results)

[figure not shown]

Figure (25): Comparison of ROC curves for discrimination between patients with TTP/HUS or SPE/HELLP using the IPF or schistocyte count.

Assessment of Immature Platelet Fraction in Pregnancy-Associated Thrombotic Microangiopathy: (Results)

Table (20): ROC curve analysis for discrimination between patients with TMA and normal controls using the IPF-%s or schistocyte count

Index	IPF-%	Schistocyte count
Positive group (TMA)	37 (64.9%)	37 (64.9%)
Negative group (normal controls)	20 (35.1%)	20 (35.1%)
Area under the ROC curve (AUC)	0.820 (0.695 to 0.909)	0.838 (0.716 to 0.922)
z statistic	5.678	8.660
P-value	<0.0001¶	<0.0001¶
Associated cut-off criterion	>8.1 %	>0 %
Sensitivity (%)	86.49 (71.2 - 95.5)	67.57 (50.2 - 82.0)
Specificity (%)	65.00 (40.8 - 84.6)	100.00 (83.2 - 100.0)
Positive predictive value (PPV, %)	82.1 (66.5 - 92.5)	100.0 (86.3 - 100.0)
Negative predictive value (NPV, %)	72.2 (46.5 - 90.3)	62.5 (43.7 - 78.9)

Diagnostic indices are presented as value (95% CI).

¶DeLong method.

- **(ROC) curve analysis for discrimination between patients with TMA or control using the IPF-%:** The optimal cutoff values for IPF-% for discrimination between patients with TMA or control was >8.1%. The sensitivity and specificity were 86.49% and 65%, respectively. The positive predictive value (PPV) and negative predictive value (NPV) were 82.1 % and 72.2%, respectively (**Table 20**), (**Figure 26**).

Assessment of Immature Platelet Fraction in Pregnancy-Associated Thrombotic Microangiopathy: (Results)

[figure not shown]

Figure (26): ROC curve for discrimination between patients with TMA and normal controls using the IPF.

- **(ROC) curve analysis for discrimination between patients with TMA or control using schistocyte count:** The optimal cutoff values for schistocyte count for discrimination between patients with TMA and normal controls was >0 %. The sensitivity and specificity were 67.57 % and 100%, respectively. The PPV and NPV were 100 % and 62.5%, respectively (**Table 20**), (**Figure 27**).

Assessment of Immature Platelet Fraction in Pregnancy-Associated Thrombotic Microangiopathy: (Results)

[figure not shown]

Figure (27): ROC curve for discrimination between patients with TMA and normal controls using the schistocyte count.

- **Comparison of the receiver-operating characteristic (ROC) curves:**

Comparison of the receiver-operating characteristic (ROC) curves between IPF-% or schistocyte count for discrimination between patients with TMA and normal controls revealed no significant difference between IPF and schistocyte count regarding discrimination between patients with TMA and controls ($P > 0.05$) (Table 21), (Figure 28).

Table (21): ROC curves for discrimination between patients with TMA and normal controls using the IPF or schistocyte count

Index	IPF-%	Schistocyte count	Difference	z	P-value¶
Area under ROC (AUC)	0.820 (0.695 to 0.909)	0.838 (0.716 to 0.922)	0.018 (-0.105 to 0.142)	0.290	0.7722

Diagnostic indices are presented as value (95% CI).

¶DeLong method

Assessment of Immature Platelet Fraction in Pregnancy-Associated Thrombotic Microangiopathy: (Results)

[figure not shown]

Figure (28): ROC curves for discrimination between patients with TMA and normal controls using the IPF or schistocyte count.

✚ Correlation between IPF and schistocytes count with different parameters

no significant correlation was found between the IPF-% and schistocytes count in patients with SPE/HELLP, or TTP/HUS, as well as the whole TMA study group (**Figure 29**), (**Table 22**).

Table (22): Correlation between the IPF-% and schistocytes count in whole study population, patients with TMA, SPE/HELLP, or TTP/HUS, and normal controls

	Correlation between IPF % and schistocyte count		
Group	Number	Spearman rho (ρ)	P-value
TMA	37	0.231	0.169

Assessment of Immature Platelet Fraction in Pregnancy-Associated Thrombotic Microangiopathy: (Results)

SPE/HELLP	24	0.190	0.375
TTP/HUS	13	-0.058	0.851

[figure not shown]

Figure (29): Scatter plot showing the correlation between the IPF and schistocyte count in patients with SPE/HELLP or TTP/HUS.

IPF-% and schistocytes counts in TTP/HUS and SPE/HELLP using multivariate analysis

Assessment of Immature Platelet Fraction in Pregnancy-Associated Thrombotic Microangiopathy: (Results)

Multivariable binary logistic regression analysis was used for discrimination between patients with TTP/HUS or SPE/HELLP using the IPF-% and schistocyte count combined. Both IPF-% (odds ratio, 1.11; 95% CI, 1.010 to 1.220; $p=0.031$) and schistocyte count (odds ratio, 1.113; 95% CI, 1.016 to 1.219; $p=0.022$) were independent predictors for TTP/HUS.

Table (23): Multivariable binary logistic regression analysis for discrimination between patients with TTP/HUS or SPE/HELLP using the IPF and schistocyte count combined

Variable	Regression coefficient (B)	SE for B	Wald	P-value	Odds ratio (OR)	95% CI for OR
IPF (%)	0.104	0.048	4.666	0.031	1.110	1.010 to 1.220
Schistocyte count (%)	0.107	0.046	5.283	0.022	1.113	1.016 to 1.219
Constant	-3.251					

Assessment of Immature Platelet Fraction in Pregnancy-Associated Thrombotic Microangiopathy: (Results)

Table (24): Receiver-operating characteristic (ROC) curve derived from the multivariable binary logistic regression model for discrimination between patients with TTP/HUS or SPE/HELLP using the IPF-% and schistocyte count combined

Sample size	37
Positive group (TTP/HUS)	13 (35.1%)
Negative group (SPE/HELLP)	24 (64.9%)
Disease prevalence (%)	35.1
<hr/>	
Index	Value
Area under the ROC curve (AUC)	0.827 (0.667 to 0.931)
z statistic	4.385
P-value	<0.0001
Sensitivity (%)	92.3 (64.0 - 99.8)
Specificity (%)	62.5 (40.6 - 81.2)
Positive likelihood ratio (+LR)	2.46 (1.4 - 4.2)
Positive likelihood ratio (-LR)	0.12 (0.02 - 0.8)
PPV, %	57.1 (34.0 - 78.2)
NPV, %	93.7 (69.8 - 99.8)

Diagnostic indices are presented as value (95% CI).

¶DeLong method.

Assessment of Immature Platelet Fraction in Pregnancy-Associated Thrombotic Microangiopathy: (Results)

[figure not shown]

Figure (30): Discrimination between patients with TTP/HUS or SPE/HELLP using IPF-% and schistocyte count combined.

Table 24 and Figure 30 shows the results of ROC curve analysis derived from the predicted probabilities as estimated from the multivariable binary logistic regression model for discrimination between patients with TTP/HUS or SPE/HELLP using the IPF and schistocyte count combined.

Table (25): Comparison of the receiver-operating characteristic (ROC) curves for discrimination between patients with TTP/HUS or SPE/HELLP using the IPF, schistocyte count, or IPF and schistocyte count combined

Marker	AUC	95% CI
IPF-%	0.692	0.519 to 0.833
Schistocyte count	0.771	0.603 to 0.893

Assessment of Immature Platelet Fraction in Pregnancy-Associated Thrombotic Microangiopathy: (Results)

IPF-% and schistocyte count combined 0.827 0.667 to 0.931

Marker	Difference between AUCs	95% CI	Z statistic	p-value
IPF-% vs. Schistocyte count	0.079	-0.171 to 0.328	0.617	0.537
IPF-% vs. IPF and Schistocyte count combined	0.135	-0.034 to 0.303	1.569	0.117
Schistocyte count vs. IPF-% and schistocyte count combined	0.056	-0.085 to 0.197	0.780	0.435

[figure not shown]

Figure (31): Discrimination between patients with TTP/HUS or SPE/HELLP.

The model had good predictive value as evidenced by increased AUC of 0.827 (95% CI, 0.667 to 0.931). The estimated sensitivity was 92.3% (64.0% - 99.8%), specificity of 62.5% (40.6% - 81.2%), PPV of 57.1%

Assessment of Immature Platelet Fraction in Pregnancy-Associated Thrombotic Microangiopathy: (Results)

(34.0% - 78.2%), and NPV of 93.7% (69.8% - 99.8%). However, no statistically significant difference ($P > 0.05$) was revealed on comparing the AUC value of ROC curve of the combined use of IPF-% and schistocyte counts to AUC values of ROC curves of either marker alone for discrimination between patients with TTP/HUS or SPE/HELLP (Table 25, Figure 31).

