Assessment of immature platelets was introduced as a non-invasive test of real time thrombopoiesis. They are newly released in the circulation with a larger size & greater RNA content than mature platelets, and can be measured by automated hematology analyzer equipped with reticulocyte detection channel and described as immature platelet fraction (IPF-%) and absolute immature platelet count (A-IPC). A high IPF-% has been suggested as an indicator of thrombocytopenia due to rapid platelet consumption, while a low IPF-% is characteristic of bone marrow suppression states. IPF-%/A-IPC has the competency to be performed routinely and, therefore, can provide therapeutic and diagnostic feedback in the compatible life threatening conditions (**Hong et al., 2013**).

Aim of work

The aim of this work is to show the utility of estimating IPF-% and A-IPC using a reticulocyte detection channel CBC auto analyzer as a simple reproducible blood analysis to be employed in the differential diagnosis of pregnancy-associated thrombotic microangiopathic conditions.

Patients and Methods

This study aiming to show the utility of estimating IPF-% and A-IPC using a reticulocyte detection channel CBC auto analyzer as a simple reproducible blood analysis to be employed in the differential diagnosis of pregnancy-associated thrombotic microangiopathic conditions. Patients were recruited from Ain Shams University Maternity Hospital.

Study sample was 57 women and were classified into three groups:

Group 1: *SPE/HELLP group.* This group will include 24 pregnant women (gestational age of >20 weeks) who are diagnosed as having TMA with provisional diagnosis of pre-eclampsia, HELLP syndrome.

Group 2: *TTP/HUS group.* This group will include 13 pregnant women (gestational age of >20 weeks) who are diagnosed as having TMA with provisional diagnosis of TTP/HUS.

Group 3: *Control group.* This group will include 20 pregnant women (gestational age of >20 weeks) having normal pregnancy with normal blood pressure and platelet count.

Inclusion criteria

Women will be included if they are:

- Older than 20 years of age
- Pregnant with singleton intrauterine pregnancy
- More than 20 weeks of gestation

Exclusion criteria

Patients will be excluded from the study if there was any of the following:

- Congenital malformation and fetuses with chromosomal or genetic syndrome.

- Recent blood transfusion.
- Refusal to participate in the study.
- BMI <18.

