Skewed numerical will be presented presented as median (interquartile range) and inter-group differences were compared non-parametrically using the Kruskal-Wallis test.

Categorical variables were presented as number (%) and differences will be compared using Fisher's exact test.

Correlations among numerical variables will be tested non-parametrically using the Spearman rank correlation.

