Figure (12): Receiver-operating characteristic (ROC) curve for discrimination between patients with TMA and normal controls using the IPF.

Assessment of Immature Platelet Fraction in Pregnancy-Associated Thrombotic Microangiopathy: (Results)

[figure not shown]

Figure (13): Receiver-operating characteristic (ROC) curve for discrimination between patients with TMA and normal controls using the schistocyte count.

Assessment of Immature Platelet Fraction in Pregnancy-Associated Thrombotic Microangiopathy: (Results)

Table (10): Comparison of the receiver-operating characteristic (ROC) curves for discrimination between patients with TMA and normal controls using the IPF or schistocyte count

Index	Marker		Difference	z	P-value¶
	IPF	Schistocyte count			
Area under ROC (AUC)	0.820 (0.695 to 0.909)	0.838 (0.716 to 0.922)	0.018 (-0.105 to 0.142)	0.290	0.7722

Diagnostic indices are presented as value (95% CI).

¶DeLong method.

Assessment of Immature Platelet Fraction in Pregnancy-Associated Thrombotic Microangiopathy: (Results)

[figure not shown]

Figure (14): Comparison of the receiver-operating characteristic (ROC) curves for discrimination between patients with TMA and normal controls using the IPF or schistocyte count.

Assessment of Immature Platelet Fraction in Pregnancy-Associated Thrombotic Microangiopathy: (Results)

Table (11): Multivariable binary logistic regression analysis for the relation between the IPF-% and TTP/HUS with adjustment for the confounding effect of the gestational age

Variable	Regression coefficient (B)	SE for B	Wald	P-value	Odds ratio (OR)	95% CI for OR
IPF -%	0.084	0.041	4.105	0.043	1.088	1.003 to 1.179
Gestational age (weeks)	-0.064	0.087	0.539	0.463	0.939	0.792 to 1.112
Constant	-0.271					

Table (12): Multivariable binary logistic regression analysis for the relation between the schistocyte count and TTP/HUS with adjustment for the confounding effect of the gestational age

Variable	Regression coefficient (B)	SE for B	Wald	P-value	Odds ratio (OR)	95% CI for OR
Scistocyte count (%)	0.101	0.052	3.781	0.052	1.107	0.999 to 1.226
Gestational age (weeks)	-0.052	0.088	0.355	0.551	0.949	0.799 to 1.127
Constant	0.420					

Table (13): Correlation between the IPF and schistocytes count in whole study population, patients with TMA, SPE/HELLP, or TTP/HUS, and normal controls

Correlation between IPF-% and schistocyte count			
Group	Number	Spearman rho (ρ)	P-value

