Assessment of Immature Platelet Fraction in Pregnancy-Associated Thrombotic Microangiopathy: (Results)

All study population	57	0.466	0.0003
TMA	37	0.231	0.169
SPE/HELLP	24	0.190	0.375
TTP/HUS	13	-0.058	0.851
Control	20	0.000	-

[figure not shown]

Figure (15): Scatter plot showing the correlation between the IPF and schistocyte count in the whole study population. Fitted lines represent local regression smoothing (LOESS) trend lines.

Assessment of Immature Platelet Fraction in Pregnancy-Associated Thrombotic Microangiopathy: (Results)

[figure not shown]

Figure (16): Scatter plot showing the correlation between the IPF and schistocyte count in patients with TMA or normal controls. Fitted lines represent local regression smoothing (LOESS) trend lines.

[figure not shown]

Figure (17): Scatter plot showing the correlation between the IPF and schistocyte count in patients with SPE/HELLP or TTP/HUS and normal controls. Fitted lines represent local regression smoothing (LOESS) trend lines.

The results of the present study are shown in tables (14 -22) and figures (18-29).

✚ Comparison between patients with SPE/HELLP or TTP/HUS and normal controls regarding demographic features:

Assessment of Immature Platelet Fraction in Pregnancy-Associated Thrombotic Microangiopathy: (Results)

There was significant difference between the three studied groups regarding maternal age ($P < 0.05$) and high significant difference between the three groups regarding gestational age ($P < 0.001$). However, there was no significant difference between parity and previous abortions ($P > 0.05$). On applying Schéffé post-hoc test revealed no statistically significant difference among the three groups regarding maternal age ($P > 0.05$). However, regarding gestational age, the Schéffé test has revealed a significant difference between either patient group (SPE/HELLP or TTP/HUS) versus control group ($P < 0.05$ for each) (**Table 14**).

Assessment of Immature Platelet Fraction in Pregnancy-Associated Thrombotic Microangiopathy: (Results)

Table (14): Characteristics of patients with SPE/HELLP or TTP/HUS and normal controls

Variable	SPE/HELLP (n=24)	TTP/HUS (n=13)	Control (n=20)	F/ χ^2	DF	p-value
Age (years)	29.5 ± 5.6	25.3 ± 4.5	26.0 ± 4.6	4.086	2, 54	0.022¶†
Parity						
P0	6 (25.0%)	2 (15.4%)	5 (25.0%)	0.213	1	0.645§
P1	5 (20.8%)	7 (53.8%)	5 (25.0%)			
P2	8 (33.3%)	2 (15.4%)	6 (30.0%)			
P3	2 (8.3%)	1 (7.7%)	3 (15.0%)			

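### Gestational age is adjusted for only in Tables 11-12, where it differs by 0.7 weeks; the IPF-% comparisons with controls, where it differs by about 6 weeks, are unadjusted

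*SAP*

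**What the plan says.** - **Adjustment made.** SAP Table (11) is titled "Multivariable binary logistic regression analysis for the relation between the IPF-% and TTP/HUS with adjustment for the confounding effect of the gestational age". Table (12) does the same for the schistocyte count. The outcome in both is TTP/HUS; neither states the comparator or the number of women.
- **Adjustment not made.** SAP Tables (9) and (20) give single-marker ROC results for 37 TMA patients against 20 controls: IPF-% AUC 0.820 (95% CI 0.695 to 0.909). The text concludes: "The optimal cutoff values for IPF-% for discrimination between patients with TMA or control was >8.1" per cent. The IPF-% comparisons that include controls in Tables (5)/(16) (medians) and (6)/(17) (share above 11.2%) have no covariate either. The only other multivariable model, Table (23), contrasts TTP/HUS with SPE/HELLP and has no gestational-age term.
- **The imbalance.** SAP Tables (3) and (14) report gestational age of 30.5 ± 4.0 weeks (SPE/HELLP, n=24), 29.8 ± 5.4 (TTP/HUS, n=13) and 24.2 ± 3.2 (control, n=20), with F=14.597 and p<0.001. The text adds: "regarding gestational age, the Schéffé test has revealed a significant difference between either patient group (SPE/HELLP or TTP/HUS) versus control group".
- **Selection of controls.** Protocol, Patients and Methods, Group 3: "This group will include 20 pregnant women (gestational age of >20 weeks) having normal pregnancy with normal blood pressure and platelet count". No matching on gestational age is described.
- **Aim.** Protocol, Aim of work: IPF-% and A-IPC are "to be employed in the differential diagnosis of pregnancy-associated thrombotic microangiopathic conditions".

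**The concern.** A variable that the SAP itself calls confounding is controlled where the groups hardly differ in it, and left uncontrolled where they differ by about one and a half standard deviations. If IPF-% changes with stage of pregnancy, part of the separation between TMA patients and controls, and the position of the >8.1% cut-off, would reflect how far along the women were and not only their disease. The bias could run either way: the AUC of 0.820 could be too high or too low. The documents do not let a reader tell, because they report no relation of IPF-% to gestational age.

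**Working it through.** **1. Reproduce the SAP's own test** (n, means and SDs from Tables 3/14).
- Grand mean = (24×30.5 + 13×29.8 + 20×24.2)/57 = 28.13.
- Between-group sum of squares = 24(2.37)² + 13(1.67)² + 20(3.93)² ≈ 480.0.
- Within-group sum of squares = 23(4.0)² + 12(5.4)² + 19(3.2)² = 912.5, so the mean square is 912.5/54 = 16.90.
- F = (480.0/2)/16.90 = 14.20. Rounding of the inputs allows 13.42 to 15.03, which contains the stated 14.597.

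**2. Where the gap lies.** Schéffé F = (difference)²/[2×16.90×(1/n₁+1/n₂)], on 2 and 54 DF.

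| Contrast | Gap (weeks) | F | p |
|---|---|---|---|
| SPE/HELLP vs TTP/HUS | 0.7 | 0.12 | 0.89 |
| SPE/HELLP vs control | 6.3 | 12.81 | <0.001 |
| TTP/HUS vs control | 5.6 | 7.31 | 0.002 |

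The pooled TMA mean is (24×30.5 + 13×29.8)/37 = 30.25 weeks, SD 4.48. The gap to controls is 6.05 weeks. The standardised difference is 6.05/4.08 = 1.48 (pooled SD) or 6.05/3.89 = 1.56 (average variance).

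**3. Which women are in Tables 11-12?** As an approximation, set the fitted logit at the means equal to the observed log-odds and solve for the mean of the marker.
- If n=37: log-odds ln(13/24) = -0.613, mean gestational age 30.25. Table 11: (-0.613 + 0.271 + 0.064×30.25)/0.084 ≈ 19.0% IPF. Table 12: (-0.613 - 0.420 + 0.052×30.25)/0.101 ≈ 5.3% schistocytes. Both are plausible.
- If n=57: log-odds ln(13/44) = -1.219, mean gestational age 28.13. Table 11 gives about 10.1%; Table 12 gives about -1.7%, which is impossible.

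The negative gestational-age coefficients also fit n=37, where TTP/HUS is 0.7 weeks earlier than its comparator; with n=57 it would be 2.2 weeks later. So 37 is likely, but it is an inference.

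**4. How far could adjustment move the AUC?** This is an illustration only, because the within-group correlation r of IPF-% with gestational age is not reported. Assume r is common to all groups and that IPF-% is normal within groups after some monotone transformation. The reported AUC gives d = √2 × Φ⁻¹(0.820) = 1.295. Adjusted AUC = Φ[(d - r×SMD)/√(2(1-r²))], with SMD 1.48 to 1.56.

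| Assumed r | Adjusted AUC |
|---|---|
| -0.3 | 0.90 |
| -0.1 | 0.85 |
| 0 | 0.82 |
| +0.1 | 0.79 |
| +0.3 | 0.73-0.74 |

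All lie within the reported 0.695 to 0.909. Stronger assumed correlations fall outside it (SMD 1.48: r=-0.4 gives 0.93, r=+0.5 gives 0.67), still above 0.5.

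**5. Price of adjusting.** For a linear model of IPF-% on group and gestational age, the between-group (TMA vs control) sum of squares for gestational age is (37×20/57)×6.05² ≈ 476 and the within-group sum is 36×4.48² + 19×3.2² ≈ 917. R² = 476/(476+917) = 0.342, variance inflation 1/(1-0.342) = 1.52, standard-error ratio √1.52 = 1.23 if IPF-% is unrelated to gestational age.

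**6. Why not the AUC of a combined model.** With r=0 the combined separation is √(1.295² + 1.48²) = 1.97, so the AUC is Φ(1.97/√2) ≈ 0.92 (about 0.93 in a simulation with 37 and 20 women). IPF-% alone is still 0.82; the rise comes from gestational age.

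**The case against.** **The gap is already reported.** A reader might infer that it is hidden. It is not: Tables 3 and 14 give it and the text states it. What is missing is the link to the AUC and cut-off. The SAP document contains results only, so one cannot say that a caveat is absent from the full thesis either.

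**No bias is shown.** This stands. Confounding needs a relation between gestational age and IPF-%, and none is reported. An imbalance, however large, does not say how much of 0.820 is due to it. Nor does the protocol's general sentence, "Correlations among numerical variables will be tested non-parametrically using the Spearman rank correlation", promise this particular correlation.

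**Tables 11-12 may belong to a replaced set.** The SAP text points to Tables 14-22 for the results. These largely repeat Tables 3-10 and 13, and nothing in Tables 14-25 corresponds to Tables 11-12. The document does not mark the earlier tables as withdrawn. If they were, the later set would contain no gestational-age adjustment at all, and the control comparison would be just as unadjusted.

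**Adjustment cannot settle the matter.** This stands in part. An observed r of zero in 57 women would have 95% limits of about ±tanh(1.96/√53) = ±0.26, equivalent to adjusted AUCs of about 0.75 to 0.89 before sampling error in the AUC itself. That argues for presenting the adjusted result as a sensitivity analysis, not for omitting it.

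**Scope.** The stated aim is differential diagnosis among TMA conditions, so the control comparison is subsidiary on that reading, although the documents give no formal hierarchy. Tables 10 and 21 compare two markers in the same women and are not the main target.

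**Conclusion.** The inconsistency is real: adjustment at a gap of 0.7 weeks, none at 6.05 weeks (1.48 to 1.56 SD). It bears on the IPF-% AUC and >8.1% cut-off in Tables 9/20 and on the control contrasts in Tables 5/16 and 6/17.

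A reader might infer that the AUC of 0.820 is mainly an effect of stage of pregnancy. The documents do not support that. Existence and direction of bias are both unknown, and with assumed correlations of -0.3 to +0.3 the adjusted AUC stays between about 0.90 and 0.73, so discrimination is not removed. Those figures rest on the assumed r, a common slope and the binormal form. A reader might also extend the doubt to TTP/HUS vs SPE/HELLP; the control gap does not touch that contrast.

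The point therefore concerns a subsidiary result that should be labelled and checked. That Tables 11-12 use the 37 patients is likely but not stated.

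**What to change.** 1. Beside Tables 9 and 20, and in the text giving the cut-off, add a note such as: *IPF-% AUC and >8.1% cut-off not adjusted for gestational age (mean 30.25 weeks in TMA patients, 24.2 in controls; Tables 3 and 14).* The same note serves the control contrasts in Tables 5/16 and 6/17.
2. Report the within-group correlation of IPF-% with gestational age.
3. Report one TMA-vs-control analysis of IPF-% adjusted for gestational age: a logistic model of IPF-% plus gestational age, or a covariate-adjusted AUC (IPF-% after removal of its within-group gestational-age trend). Do not use the AUC of the combined model's predicted probabilities. Present it as a sensitivity analysis.
4. State the comparator and n in Tables 11 and 12.

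Cost: a footnote, one correlation and one two-predictor analysis (20 women in the smaller group), all from data already collected. The downside is precision and overlap. The standard error is about 23% larger. Under distributions matched to the reported means and SDs, only about 1 of 20 controls lies above 30 weeks, against about 19 of 37 TMA patients, so the adjusted result leans on extrapolation at later gestations.
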